## 11. MEASUREMENT OF EFFECT

Although response is not the primary endpoint of this trial, patients with measurable disease will be assessed by standard criteria. For the purposes of this study, patients should be re-evaluated

at week 11 just prior to surgical therapy. After surgical therapy, only recurrence will be documented. Surgical and pathologic findings will be used to confirm response assessment at 11 weeks.

### 11.1 Antitumor Effect – Solid Tumors

Response and progression will be evaluated in this study using the new international criteria proposed by the Response Evaluation Criteria in Solid Tumors (RECIST) Committee (version 1.1) [[Eur J Cancer](#), 2009 Jan;45(2):228-47]. Changes in only the largest diameter (unidimensional measurement) of the tumor lesions are used in the RECIST criteria.

#### 11.1.1 Definition

Evaluable for toxicity. All patients will be evaluable for toxicity from the time of their first treatment with AZD6244.

Evaluable for objective response. Only those patients who have measurable disease present at baseline, have received a complete treatment, and have had their disease re-evaluated will be considered evaluable for response. These patients will have their response classified according to the definitions stated below. (Note: Patients who exhibit objective disease progression prior to the end of treatment will also be considered evaluable.)

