### 1.2. Secondary Objectives

- To determine if changes in phosphorylated ERK (pERK) in peripheral blood mononuclear cells correlates to changes in pERK in rectal tumors in the setting of treatment with AZD6244.
- To obtain exploratory information regarding the pathologic complete response rate (pCR) obtained after treatment with the MTD of AZD6244 Hyd-Sulfate in combination with Capecitabine and 50.4 Gy of radiation.
- To determine if a reduction in phosphorylated ERK (pERK) in peripheral blood mononuclear cells correlates to similar changes in ERK phosphorylation in rectal tumors in the setting of treatment with AZD6244.
- To perform an exploratory analysis to determine if the presence of activating mutations in *RAS* or *BRAF* in tumor or changes in plasma transforming growth factor- $\alpha$  (TGF $\alpha$ ) levels and tumor pERK/total ERK with AZD6244 treatment alone and after AZD6244 in combination with Capecitabine and radiation predicts for tumor/nodal down staging or pCR

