## 2.2 **Other Agent(s)**

Capecitabine and radiation are frequently combined for the treatment of gastrointestinal malignancies. Capecitabine is a fluoropyrimidine carbamate that is an orally administered prodrug of 5'-deoxy-5-fluorouridine (5'-DFUR) that is converted to 5-fluorouracil (5-FU). 5'-DFUR is hydrolyzed to the active drug 5-FU by thymidine phosphorylase which is present in many tissues in the body. Thymidine phosphorylase is expressed in higher concentrations in some human carcinomas compared to surrounding tissues.

In the setting of rectal cancer, there is a growing experience of Capecitabine and radiotherapy in the neoadjuvant setting.(18) The maximum tolerated dose of Capecitabine is 800-825 mg/m^2 twice daily combined with 50.4 Gy of radiation.(19-22) Downstaging occurs in approximately 50-85% of patients receiving the combination of Capecitabine and radiation in the neoadjuvant setting for locally advanced rectal cancer. Pathologic complete response rates of 8-16% have been described with the combination, similar to that observed with the combination of 5-FU and radiation in this setting.(23, 24) The most common Grade 3 or higher toxicity observed with Capecitabine in this setting is diarrhea which may be observed in as many as 20% of patients.

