#### 4.1.4 Surgery

Surgery is not part of this protocol. It is anticipated that at the completion of chemoradiation patients will have a four to six week recovery period and will undergo surgical resection as is the current clinical standard. Surgical specimens will be reviewed by the Surgical Pathology laboratory at NIH for examination and determination of response.

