### 11.2 Other Response Parameters

Pathologic complete response will be assessed on surgical specimens. This will include an evaluation of evidence of residual gross and microscopic disease in the resected rectum and

lymph nodes.

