### 13.3 Analysis of Secondary Endpoints

The secondary endpoints include pathologic CR at the time of surgical resection, pERK/total ERK in PBMC and tumor, plasma TGF $\alpha$  level, pharmacokinetics of AZD6244 alone compared to in combination with capecitabine, and presence of mutations in tumor biopsies. Analysis of secondary endpoints will focus on samples obtained at the MTD (12 patients) with the goal of describing potentially useful measures for future testing in Phase II trials of sufficient power. Changes in TGF $\alpha$  level from pre to post treatment will be related to the probability of pathologic CR using logistic regression. Presence of activating *BRAF* or *RAS* mutations or inactivating *PTEN* mutations in tumor biopsies pretreatment will be related to the probability of pathologic CR using logistic regression. We will evaluate if a reduction in pERK in PBMC (flow cytometry) correlates to a reduction in pERK in tumor (IHC grading) after AZD6244 treatment with a Spearman Rank Correlation.

The final PK analyses will be the responsibility of Clinical Pharmacology and DMPK, Alderley Park, AstraZeneca, UK. The AZD6244, N-desmethyl and AZD6244 amide concentration-time data, along with the derived PK parameters, will be listed and summarized appropriately. Where data allow, the following PK parameters will be

determined following administration of AZD6244 alone and following administration of AZD6244 alone and AZD6244 & capecitabine together. Additional parameters may be determined if deemed appropriate:

AZD6244:  $C_{max}$ ,  $t_{max}$ ,  $AUC_{(0-12)}$ ,  $AUC_{(0-24)}$ ,  $AUC_{(0-t)}$ ,  $C_{min}$ ,  $CL/F$

N-desmethyl AZD6244 and AZD6244 amide:  $C_{max}$ ,  $t_{max}$ ,  $AUC_{(0-12)}$ ,  $AUC_{(0-24)}$ ,  $AUC_{(0-t)}$ ,  $C_{min}$ ,  $CL/F$ , AUC metabolite:parent ratio,  $C_{max}$  metabolite:parent ratio

The PK parameters will be derived using non-compartmental analysis. The maximum plasma concentrations ( $C_{max}$ ) and the time to reach the maximum plasma concentrations ( $t_{max}$ ) will be determined by visual inspection of the plasma concentration-time profiles. The area under the plasma concentration-time curve from zero to 12 hours post dose  $AUC_{(0-12)}$  and zero to 24 hours post-dose  $AUC_{(0-24)}$  will be calculated by the linear trapezoidal rule. The total oral clearance from plasma ( $CL/F$ ) after an oral dose will be calculated from the dose divided by the AUC during the appropriate dosing interval.

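### Objective response leaves out patients who stop all treatment early or are not re-evaluated, and the pCR rate has no stated denominator

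*Combined protocol and SAP*

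**What the plan says.** **Objective response.** Section 11.1.1 restricts the evaluable set to patients who have measurable disease at baseline and who "have received a complete treatment, and have had their disease re-evaluated will be considered evaluable for response". A note directly after this adds: "Patients who exhibit objective disease progression prior to the end of treatment will also be considered evaluable". The same section makes every patient evaluable for toxicity from the first AZD6244 dose. No section says what counts as a complete treatment.

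**pCR.** Section 11.2 says "Pathologic complete response will be assessed on surgical specimens", and Section 4.1.4 says "Surgery is not part of this protocol", while anticipating resection after a recovery period. Neither says how a patient without a resection enters the rate. Section 13.3 comes nearest to a denominator: "Analysis of secondary endpoints will focus on samples obtained at the MTD (12 patients").

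**Rank of the endpoints.** Section 11 opens with "Although response is not the primary endpoint of this trial". The pCR objective in Section 1.2 reads "To obtain exploratory information regarding the pathologic complete response rate (pCR) obtained after treatment with the MTD". Section 13.3 sets no test, power or threshold for either rate. Section 2.2 gives background figures for capecitabine with radiation: "Pathologic complete response rates of 8-16% have been described with the combination".

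**The concern.** Membership of the objective-response set depends on events after the start of treatment, and some of those events can be caused by the drug under study. Section 4.4 lists the ways in which AZD6244 can end: toxicity, progression, intercurrent illness, unacceptable adverse events, withdrawal and investigator judgment. Only progression has a clause that keeps the patient in the response set. Someone who stops everything for toxicity in week 3 therefore counts toward harm but not toward response.

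For pCR the problem is silence. An unresected patient has no specimen, so a rate built from the available specimens would omit that patient without anyone having decided to do so. The logistic regressions of pCR on TGF-alpha change and mutation status in Section 13.3 have the same gap, because an unresected patient has no outcome.

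At stake is how the activity description at the MTD reads when a phase II trial is considered. An undefined completeness criterion also lets inclusion be settled case by case once the response is known.

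**Working it through.** **1. Who stays in and who leaves under the text as written**

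| Patient | Objective response (11.1.1) | pCR (11.2, 13.3) |
|---|---|---|
| Finishes treatment, re-evaluated at week 11, resected | In | In |
| Objective progression before end of treatment | In, by the note | Not stated if unresected |
| Stops or reduces AZD6244 for a DLT, finishes chemoradiation, re-evaluated | Unclear: complete treatment undefined | In if resected |
| Stops all treatment for toxicity, illness or withdrawal | Out | Not stated if unresected |
| Finishes treatment but not re-evaluated | Out | In if resected |
| Finishes treatment, re-evaluated, not resected | In | Not stated |

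The third row is open because Sections 4.4 and 13.1 have DLT patients continue capecitabine and radiation, and Section 5.1 provides for AZD6244 reductions, but nothing links these cases to the evaluability rule.

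The progression note has limited reach. The study calendar in Section 10 schedules tumor measurements and CT pre-study and at week 11, with treatment in weeks 1 to 7, so no tumor imaging is scheduled while the note could apply. Patients who deteriorate without objective evidence of progression are reported separately under Section 11.1.4.3, and the note does not cover them.

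**2. The plan's own figure**

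The 12 patients at the MTD reproduce from Section 13.1: 6 to establish the dose plus 6 in the expansion, 6 + 6 = 12. The documents give no expected dropout, non-resection or response rate for this trial, so the counts below are assumptions.

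**3. Size of the effect**

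If x of 12 respond and k non-responders are left out, the reported rate is x/(12-k) instead of x/12, a ratio of 12/(12-k). For an illustrative x = 2, with exact (Clopper-Pearson) 95% intervals:

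| k left out | Rate | Ratio to 2/12 | Exact 95% interval |
|---|---|---|---|
| 0 | 2/12 = 16.7% | 1.00 | 2.1 to 48.4% |
| 1 | 2/11 = 18.2% | 1.09 | 2.3 to 51.8% |
| 2 | 2/10 = 20.0% | 1.20 | 2.5 to 55.6% |
| 3 | 2/9 = 22.2% | 1.33 | 2.8 to 60.0% |

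The shifts are 1.5, 3.3 and 5.6 percentage points (from unrounded rates). With x = 1 the rate moves from 8.3% to 9.1%, 10.0% and 11.1%.

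Applied to the ends of the background range in Section 2.2, with k = 1 to 3:
- 8% is 0.96 expected of 12, and becomes 8.7%, 9.6% and 10.7%.
- 16% is 1.92 expected of 12, and becomes 17.5%, 19.2% and 21.3%.

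**4. Objective response, illustrated**

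Assume 12 treated patients with measurable disease, 6 responders, 2 who stop all treatment for toxicity and 1 early objective progressor.
- All treated: 6/12 = 50.0%.
- Section 11.1.1 as written (2 toxicity stops out, progressor kept): 6/10 = 60.0%.

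**The case against.** The strongest reply is that the documents say less than a critical reader may take from them. Four stronger readings are tempting, and none is supported.

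- **Progressors drop out.** Not for objective response: the note in Section 11.1.1 keeps objective progressors. In the illustration above, removing the progressor as well would give 6/9 = 66.7%, but that is not the plan's rule.
- **A DLT removes the patient.** Sections 4.4 and 13.1 have such patients continue capecitabine and radiation, so they can reach week 11 and resection. Whether they count as complete is ambiguous, which is different from exclusion. The MTD also requires no more than 1 DLT in 6 patients, so few are expected at that dose.
- **The pCR rate is biased upward.** The completeness rule belongs to objective response. Section 11.2 says only where pCR is read, and the one number in Section 13.3 is 12, the full MTD group. Non-resection may also be uncommon: Section 3.3.2 reviews CT for resectable disease and Section 3.3.5 requires a surgical consultation for all.
- **Exclusions push pCR clear of 8 to 16%.** With two pCRs, 2/12 = 16.7% is already above 16%, and every interval in the table contains the whole range. No comparison with that range is planned, and the documents do not show whether the background rates used resected or all treated patients.

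All four replies stand. They do not remove the exclusion that Section 11.1.1 does state, or supply the missing pCR denominator. More patients would narrow the interval but would not remove a shift caused by the choice of denominator.

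**Conclusion.** The point holds in a limited form. For objective response there is a stated rule that removes patients who stop all treatment for reasons other than objective progression, or who are not re-evaluated. It raises the rate when those patients are non-responders, and the key term in it is undefined. For pCR there is an omission: nothing says whether unresected patients count, so upward bias is possible but not prescribed.

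The impact is small. One to three exclusions of 12 inflate the rate by a factor of 1.09 to 1.33, well inside the sampling uncertainty. Response is not primary, pCR is exploratory, and no formal decision rests on either. The size rests on assumed values of k and x and on the excluded patients being non-responders. An unresected patient's pathologic status is unknown, so a rate that counts such patients as not pCR is a lower bound.

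**What to change.** - **Section 11.1.1:** report objective response over all treated patients with measurable baseline disease, with no re-evaluation counted as non-response. Define complete treatment for analysis purposes, stating how patients who stop or reduce AZD6244 but finish chemoradiation are classified.
- **Sections 11.2 and 13.3:** report pCR over all patients treated at the MTD, with unresected patients counted as not pCR. State how unresected patients are handled in the pCR regressions.
- **Both rates:** show the evaluable or resected rate beside the all-treated rate, with the number excluded and the reason for each. A later reader can then match whichever denominator an external rate used.

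The cost is wording only: no added patients, visits or tests. The downside is that the stated rates become slightly less favourable.

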#### 11.1.2 Disease Parameters

Measurable disease. Measurable lesions are defined as those that can be accurately measured in at least one dimension (longest diameter to be recorded) as  $\geq 20$  mm with conventional techniques (x-ray) or as  $\geq 10$  mm with spiral CT scan or caliper measurements by clinical exam. Lymph nodes must be  $\geq 15$  mm in short axis by CT to be considered measurable (for lymph nodes only short axis will be followed). All tumor measurements must be recorded in millimeters (or decimal fractions of centimeters).

Non-measurable disease. All other lesions (or sites of disease), including small lesions (longest diameter  $< 10$  mm or pathological lymph nodes with short axis  $< 15$  mm are considered non-measurable disease. Bone lesions, leptomeningeal disease, ascites, pleural/pericardial effusions, lymphangitis cutis/pulmonis, inflammatory breast disease, abdominal masses (not followed by CT or MRI), and cystic lesions are all non-measurable.

Target lesions. All measurable lesions up to a maximum of 5 lesions per organ and 10 lesions in total, representative of all involved organs, should be identified as **target lesions** and recorded and measured at baseline. Target lesions should be selected on the basis of their size (lesions with the longest diameter) and their suitability for accurate repeated measurements (either by imaging techniques or clinically). A sum of the longest diameter (LD) for all target lesions will be calculated and reported as the baseline sum LD. The baseline sum LD will be used as reference by which to characterize the objective tumor response.

Non-target lesions. All other lesions (or sites of disease) including any measurable

lesions over and above the 10 target lesions should be identified as **non-target lesions** and should also be recorded at baseline. Measurements of these lesions are not required, but the presence or absence of each should be noted throughout follow-up.

#### 11.1.3 Methods for Evaluation of Measurable Disease

All measurements should be taken and recorded in metric notation using a ruler or calipers. All baseline evaluations should be performed as closely as possible to the beginning of treatment and never more than 4 weeks before the beginning of the treatment.

The same method of assessment and the same technique should be used to characterize each identified and reported lesion at baseline and during follow-up. Imaging-based evaluation is preferred to evaluation by clinical examination when both methods have been used to assess the antitumor effect of a treatment.

Clinical lesions Clinical lesions will only be considered measurable when they are superficial and  $\geq 10$  mm in diameter (e.g., skin nodules). In the case of skin lesions, documentation by color photography, including a ruler to estimate the size of the lesion, is recommended.

Chest x-ray Lesions on chest x-ray are acceptable as measurable lesions when they are clearly defined and surrounded by aerated lung. However, CT is preferable.

Conventional CT and MRI These techniques should be performed with cuts of 5 mm or less in slice thickness contiguously. This applies to tumors of the chest, abdomen, and pelvis. Head and neck tumors and those of extremities usually require specific protocols. MRI is acceptable in certain situations.

Ultrasound (US) When the primary endpoint of the study is objective response evaluation, US should not be used to measure tumor lesions. It is, however, a possible alternative to clinical measurements of superficial palpable lymph nodes, subcutaneous lesions, and thyroid nodules. US might also be useful to confirm the complete disappearance of superficial lesions usually assessed by clinical examination.

Endoscopy, Laparoscopy The utilization of these techniques for objective tumor evaluation has not yet been fully and widely validated. Their uses in this specific context require sophisticated equipment and a high level of expertise that may only be available in some centers. Therefore, the utilization of such techniques for objective tumor response should be restricted to validation purposes in reference centers. However, such techniques may be useful to confirm complete pathological response when biopsies are obtained.

Tumor markers Tumor markers alone cannot be used to assess response. If markers are initially above the upper normal limit, they must normalize for a patient to be considered in complete clinical response. Specific additional criteria for standardized usage of prostate-specific antigen (PSA) and CA-125 response in support of clinical

trials are being developed.

Cytology, Histology These techniques can be used to differentiate between partial responses (PR) and complete responses (CR) in rare cases (e.g., residual lesions in tumor types, such as germ cell tumors, where known residual benign tumors can remain).

The cytological confirmation of the neoplastic origin of any effusion that appears or worsens during treatment when the measurable tumor has met criteria for response or stable disease is mandatory to differentiate between response or stable disease (an effusion may be a side effect of the treatment) and progressive disease.

#### 11.1.4 Response Criteria

##### 11.1.4.1 Evaluation of Target Lesions

Complete Response (CR): Disappearance of all target lesions. Any pathological lymph nodes (whether target or non-target) must have reduction in short axis to <10 mm.

Partial Response (PR): At least a 30% decrease in the sum of the longest diameter (LD) of target lesions, taking as reference the baseline sum LD

Progressive Disease (PD): At least a 20% increase in the sum of the LD of target lesions, taking as reference the smallest sum LD recorded since the treatment started or the appearance of one or more new lesions

Stable Disease (SD): Neither sufficient shrinkage to qualify for PR nor sufficient increase to qualify for PD, taking as reference the smallest sum LD since the treatment started

##### 11.1.4.2 Evaluation of Non-Target Lesions

Complete Response (CR): Disappearance of all non-target lesions and normalization of tumor marker level. All lymph nodes must be non-pathological in size (<10mm short axis).

Note: If tumor markers are initially above the upper normal limit, they must normalize for a patient to be considered in complete clinical response.

Incomplete Response/Stable Disease (SD): Persistence of one or more non-target lesion(s) and/or maintenance of tumor marker level above the normal limits

Progressive Disease (PD): Appearance of one or more new lesions and/or unequivocal progression of existing non-target lesions

Although a clear progression of “non-target” lesions only is exceptional, the opinion of the treating physician should prevail in such circumstances, and the progression status should be confirmed at a later time by the review panel (or

Principal Investigator).

#### 11.1.4.3 Evaluation of Best Overall Response

The best overall response is the best response recorded from the start of the treatment until disease progression/recurrence (taking as reference for progressive disease the smallest measurements recorded since the treatment started). The patient's best response assignment will depend on the achievement of both measurement and confirmation criteria.

Target Lesions	Non-Target Lesions	New Lesions	Overall Response
CR	CR	No	CR
CR	Non-CR/Non-PD	No	PR
CR	Not evaluated	No	PR
PR	Non-PD or not all evaluated	No	PR
SD	Non-PD or not all evaluated	No	SD
Not all evaluated	Non-PD	No	NE
PD	Any	Yes or No	PD
Any	PD*	Yes or No	PD
Any	Any	Yes	PD

\* In exceptional circumstances, unequivocal progression in non-target lesions may be accepted as disease progression.

Note: Patients with a global deterioration of health status requiring discontinuation of treatment without objective evidence of disease progression at that time should be reported as “*symptomatic deterioration*”. Every effort should be made to document the objective progression even after discontinuation of treatment.  
CR = complete response, PR = partial response, SD = stable disease, PD = progressive disease, and NE = inevaluable.

